5.3 Postoperative

All patients will be given identical postoperative instructions:

- Minimize activity of the involved extremity (no exercises, no abduction beyond 90)
- No lifting of objects weighing more than 10 pounds
- May shower after 48 hours

Serous drainage will be measured daily by the patient/family/home health agency and recorded on the provided data sheet. The axillary drain will be removed once the cumulative serous drainage volume ≤ 30 ml / 24 hours for 2 days or maximum of 21 days has elapsed since surgery.

The first post-op day, all patients will have a 10 cc specimen of blood obtained and the contents of the drain will be collected.

5.4 Laboratory Correlates

The laboratory studies will be performed under the direction of [name]. (Departments of Surgical Oncology and Cancer Biology). Specified blood samples pre- and postoperatively will be obtained by qualified personnel and processed for serum. VEGF-D and VEGF-C serum levels will be measured by enzyme-linked immunosorbent assay (ELISA). Lymph fluid will also be analyzed for these growth factors using ELISA kits as well. Skin specimens will be analyzed for VEGF-C, VEGF-D, VEGFR-3 expression by immunohistochemical staining.

6.0 Pretreatment Evaluation

6.1 A complete history including age and smoking history will be obtained within 2 weeks of randomization. Past medical history will record any history of connective tissue disorders, diabetes or medication usage.

6.2 Physical examination including height and weight will be recorded within 2 weeks of surgery.

6.3 Pregnancy test for women of child-bearing potential if indicated.

7.0 Follow-Up Data Collection

7.1 Wound Surveillance

Inpatients – For patients who are admitted to the hospital, the wound will be monitored by the surgeon for evidence of wound complications (bleeding, skin necrosis, hematoma, etc.) in the first 24 hours after surgery and daily until discharge.

Outpatients – The patients will be instructed in catheter care according to nursing protocol. The amount of drainage must be recorded for each day (24 hour period) including the day the drain is removed.

Drain Removal – Drains will be removed once the cumulative serous drainage drops to ≤ 30 ml / 24 hours for 2 consecutive days or a maximum of 21 days for axillary node dissection. Removal of the drain may be performed at an outside institution by a local physician once the criteria have been reached. Patients will be instructed to contact the protocol research nurse to verify that drain removal criteria have been met prior to removal.

Follow-Up - Follow-up wound examination will be performed by the local primary physician or in the MDACC Melanoma Clinic between 1-4 weeks post-op and at approximately 6 weeks following surgery. A 10 cc specimen of blood will be obtained 2-3 weeks and 3-6 months after surgery. The contents of the drain will be collected from patients during the first day after surgery, during the first return follow-up visit to M.D. Anderson Cancer Center, and during drain removal (unless these latter 2 dates are the same). A voluntary 4 mm punch biopsy will be performed using local anesthesia on patients within the first 6 months of follow-up.

7.2 Secondary Objectives

Postoperative complications will be recorded by the protocol nurse and verified by the attending surgeon. Specific clinical information including occurrence of fever with symptoms or signs of infection, will be obtained by telephone if the patient is unavailable for a clinic visit.

Wound infection will be defined by the following criteria:

Culture positive seroma aspirate with clinical evidence of infection (i.e. fever, cellulitis)

Cellulitis as judged by a clinician requiring antibiotics or more aggressive wound management and responding appropriately to treatment.

Clinically significant postoperative seroma formation will be ascertained at a 6 week follow-up visit or telephone contact. Seroma will be defined as a fluid collection in the axilla that is symptomatic and requires treatment with a drainage procedure (i.e. aspiration).

8.0 Data Collection Tools

Part I - Pilot questionnaire (Appendix G) will be used.

Part II - Data sheets (Appendices A and B) will be used to capture patient information including:

Preoperative Assessment:

Risk Factors: smoking, obesity (BMI > 30)

Prior therapy

Date of randomization

Intraoperative Assessment:

Surgeon
 Date of procedure
 Perioperative antibiotics
 Procedure performed
 Indication (i.e., after positive sentinel node biopsy or for clinically evident disease)
 Estimated blood loss
 Length of operation

Post-Operative Assessment:

Date of drain removal
 Wound complications: infection, seroma, wound necrosis or dehiscence, clogged drain, hematoma, etc.
 Final pathologic assessment: diagnosis, number of nodes examined, number of tumor involved nodes
 Tumor stage

Patients will be instructed in catheter care according to nursing protocol and given instructions on completing the drain output forms. The amount of drainage will be recorded for each day (24 hour period) including the day the drain is removed.

Part II - Willingness-to-pay preoperative questionnaire 1A and willingness-to-pay postoperative questionnaire 1B (Appendix H) will be used.

9.0 Statistical Considerations

This is a single-institution, randomized, phase III trial of the fibrin tissue adhesive (TISSEEL®) versus no fibrin tissue adhesive (control) in patients with melanoma undergoing nodal dissection of the axilla. The primary outcome, is time-to-drain removal (T). The null median for the group based on historical experience without fibrin glue is 14 days (Table 1) with an accrual rate of 7 patients per month. A group-sequential design with up to two tests using O'Brien-Fleming early stopping boundaries for both superiority and futility will be used, with overall type I error probability .01 and power .95 will be used. The goal will be to detect a 4 day drop in mean time-to-drain removal. A maximum of 95 patients will be accrued to obtain a sample size of 90 assuming a 5% rate of patients who are inevaluable. Based on a two-sample Z-score test statistic, within in each subgroup the interim test cutoffs will be +/- 3.64 to reject the null hypothesis of no difference and +/- .632 to stop for futility, with a final test cutoff of +/- 2.57 to reject the null. The anticipated study duration will be roughly 12 months.

Table 1.

Subgroup	Disease	Type of Surgery	Accrual Rate (patients/month)	Historical Median # Days to Drain Removal
1	Melanoma	Axillary node dissection	7	14

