4.3 Part II - Exclusion Criteria

Patients with known hypersensitivity to bovine proteins.

Patient has undergone prior radiation therapy to the operative site.

Patient is pregnant or lactating.

Patient is steroid dependent within prior 6 months.

Patient has used aspirin or other anti-platelet drug (excluding Celebrex) within seven days of operation.

Patient has pre-existing lymphedema.

Patient has other pre-existing medical conditions with evidence of organ dysfunction as determined by principal investigator.

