5.1 Preoperative

After consents for operation and study participation are signed, patients will be registered for the trial by the research nurse. Patients will be randomized using a computerized randomization scheme.

Patients will be randomized to two groups:

Group I Treatment Group: Patients will receive fibrin sealant following completion of axillary dissection.

Group II Control Group: No fibrin sealant.

The results of the randomization will remain in a sealed envelope. The surgical team will be blinded until the surgical dissection is completed.

All patients will have a 10 cc specimen of blood collected prior to surgery.

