5.2 Intraoperative

Patients will be brought to the operating room within one week of randomization.

All patients will receive prophylactic antibiotic coverage at the time of surgery with Ancef or, if an allergy to cephalosporins exists, the antibiotic of choice of the surgeon.

Patients with melanoma will undergo a standard Level I-III axillary node dissection.

During surgery, a specimen of normal viable skin, full thickness, 5 mm x 3 cm from the non-margin portion or the edge of incision will be obtained. This will not impact the closure.

At the completion of the procedure, once bleeding has been controlled in the surgical site, the exposed surgical surfaces will be blotted dry. The surgeon will then be informed of the patient's randomization status.

If the patient is randomized to Group I (Treatment Group) the circulating nurse will proceed with the preparation of the TISSEEL® (Thrombin component diluted 1:100) as described in Appendix I. The product will then be applied as a thin, uniform coating over the exposed soft tissue of the chest wall and axilla.

Patients in both treatment groups will have a 19-French Blake closed suction drain inserted into the axilla and secured with a nylon suture. The wound will then be closed allowing the fibrin sealant to seal the apposed tissues.

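### Does the undefined 5% 'inevaluable' allowance in Section 9 leave the primary comparison open to biased exclusions?

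*Combined protocol and SAP*

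**What the plan says.** Section 9.0 sets the accrual ceiling in one sentence: "A maximum of 95 patients will be accrued to obtain a sample size of 90 assuming a 5% rate of patients who are inevaluable". The term is used only there. No section supplied defines it, names an intention-to-treat or other analysis set, or says how a randomised patient without a usable drain-removal time is handled.

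Other sections bear on who might be left out:

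- Section 5.1 keeps the allocation in a sealed envelope and adds: "The surgical team will be blinded until the surgical dissection is completed".
- Section 5.2 fixes the gap between allocation and surgery: "Patients will be brought to the operating room within one week of randomization".
- Section 4.3 has an exclusion that counts back from surgery, not from randomisation: "Patient has used aspirin or other anti-platelet drug (excluding Celebrex) within seven days of operation".
- Section 6.0 times the history, which includes medication use: "A complete history including age and smoking history will be obtained within 2 weeks of randomization".
- Section 5.3 leaves the daily log to people outside the trial team: "Serous drainage will be measured daily by the patient/family/home health agency and recorded on the provided data sheet".
- Section 7.1 permits removal elsewhere: "Removal of the drain may be performed at an outside institution by a local physician once the criteria have been reached". It then has patients call the research nurse first, so that the criteria can be confirmed.
- Section 8.0 lists the procedure date and the drain-removal date as data-sheet items, and requires of the log: "The amount of drainage will be recorded for each day (24 hour period) including the day the drain is removed".

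**The concern.** A plan that accrues 95 to analyse 90 expects to leave out about five randomised patients. If the reason for leaving them out is not fixed in advance, it can be settled after the surgeon knows the arm, and the choice could then depend on arm or outcome.

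Two groups look exposed. The first is patients who take an anti-platelet drug between randomisation and surgery. The exclusion window is seven days before operation and surgery can be up to a week after randomisation, so in the limiting case the whole window falls after randomisation. The second is dissected patients with an incomplete home log or a drain removed elsewhere. Section 9.0 does not say whether either group is inevaluable. Two analysts could therefore test different sets: everyone dissected, or everyone dissected less those later judged ineligible or badly recorded. Only the first set preserves the randomised comparison among dissected patients.

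**Working it through.** **1. The plan's own figure.** Inputs from Section 9.0: 90 evaluable, 5% inevaluable. 90/(1 − 0.05) = 94.7, which rounds up to 95. The stated ceiling reproduces, and the allowance is 95 − 90 = 5 patients.

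**2. Effect on power.** Section 9.0 gives a 4-day difference, a final cutoff of 2.57 and power 0.95, but no SD. Assume 1:1 allocation (45 per arm) and use the final test only.

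- SE = 4/(2.57 + 1.645) = 0.949 day.
- SD = 0.949/√(2/45) = 4.50 days.
- Power = Φ(4/(SD·√(4/N)) − 2.57).

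| Analysed | SD 4.5 (back-solved) | SD 6.0 (assumed wider) |
|---|---|---|
| 90 | 0.950 | 0.723 |
| 95 | 0.961 | 0.751 |

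If 10% were lost instead of 5%, about 86 would be analysed, with power 0.940 at SD 4.5. If all 95 were analysed and the 4-day effect were diluted by 5%, power would be 0.939. Integrating the two-look design with the stated cutoffs, with the interim assumed at half the information, gives the same powers for 90, 95 and 86 analysed to within 0.001. The definition hardly affects power; the unstated SD matters far more.

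**3. Possible bias per exclusion.** Assume arms of 47 and 48, an arm mean of 14 days (the documents give a median of 14), and an excluded patient at the 21-day maximum. Dropping k such patients from an arm of n moves that arm's mean by 14 − (14n − 21k)/(n − k).

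- k = 1: n = 47 gives 14 − 637/46 = 0.152 day; n = 48 gives 14 − 651/47 = 0.149 day.
- k = 2: n = 47 gives 14 − 616/45 = 0.311 day; n = 48 gives 14 − 630/46 = 0.304 day.

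The shift in Z is that figure divided by SD·√(1/(n − k) + 1/(95 − n)). For k = 1 it is 0.16 at SD 4.5 and 0.12 at SD 6.0. For k = 2 it is 0.33 and 0.24 to 0.25.

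Section 2.0 quotes drain times of 14.8 ± 9.6 and 7.9 ± 3.7 days from a breast-cancer trial. If those spreads are SDs (an assumption), their root mean square is √((9.6² + 3.7²)/2) = 7.3, and the shifts fall to about 0.10 for one patient and 0.20 to 0.21 for two. Exclusions unrelated to arm and outcome give no bias.

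**4. Can the feared exclusions arise from the text?**

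- *Never dissected.* No drain is placed, so no endpoint exists. The loss comes before the envelope is opened, so the surgical team cannot act on the arm.
- *Anti-platelet use after randomisation.* No section says a randomised patient found in breach is removed from the analysis. A breach found before or during the dissection is found blind. Harm needs three further steps: discovery after unblinding, a decision to exclude, and dependence of that decision on arm and drain time. The documents support none of them.
- *Incomplete log.* Time to removal is the difference of two dates, both on the data sheet in Section 8.0, apart from the drain output forms. A gap in daily volumes does not make it missing. The nurse contact before removal in Section 7.1 reaches patients whose drains come out elsewhere.
- *Drain still in at day 21.* Sections 5.3 and 7.1 set that as the maximum, so a drain removed then has a known time and gives no ground for exclusion. The 21-day patient in step 3 is therefore a pessimistic device, not a likely case.

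**The case for a change.** The strongest case for a change is that this goes beyond a routine request for an intention-to-treat sentence. The plan budgets for omitting patients from the primary test of a randomised trial, without saying which ones, and surgeons learn the arm once dissection ends. A few sentences in Section 9.0 would settle it, need no new data, leave 95 unchanged if the 5% rate is right, and protect the comparison only if written before outcomes are seen by arm.

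Part of this stands. The term is undefined, and a dissected patient whose removal date cannot be recovered has no stated rule. Restricting the term to patients never dissected would not solve that last case, because such a patient would be neither inevaluable nor analysable. The contact with the nurse and the recorded dates should make it uncommon. Appendices A and B were not available; they are described as data sheets and are unlikely to define an analysis population.

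What does not stand is the step from an undefined word to a biased analysis. No section gives the surgical team, or anyone who knows the arm, the task of judging evaluability, and no stated rule is shown to be wrong.

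**Conclusion.** No change to the plan follows. Section 9.0 omits a definition, but the reading that fits the design, randomised and never dissected, is harmless. An analyst would ordinarily keep every dissected patient in the assigned arm and report any missing removal dates by arm. On that reading there is no bias, and the 95/90 arithmetic holds.

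If a dissected patient were nonetheless dropped, one net exclusion at the 21-day maximum would move the difference by about 0.15 day and Z by about 0.10 to 0.16, against 2.57. This rests on assumed 1:1 allocation, an arm mean of 14 days and an SD between 4.5 and 7.3 days; the plan states none of these. It would matter only for a result already close to the cutoff. The conclusion would differ if the documents provided for excluding dissected patients after unblinding; they do not.

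### Should the primary test of time to drain removal adjust for smoking and BMI instead of using an unadjusted two-sample Z?

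*Combined protocol and SAP*

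**What the plan says.** Section 9.0 states the target as a difference in means ("The goal will be to detect a 4 day drop in mean time-to-drain removal") and sets the error rates ("with overall type I error probability .01 and power .95 will be used"). It plans 90 evaluable patients out of 95 accrued. Both looks rest on one statistic, introduced by "Based on a two-sample Z-score test statistic". The cutoffs are 3.64 (reject) and .632 (futility) at the interim and 2.57 at the end, all two-sided. No covariate or adjusted model appears.

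Section 5.1 describes allocation only as "Patients will be randomized using a computerized randomization scheme" and names no stratification factor.

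The candidate covariates are collected elsewhere. Section 6.0 has "A complete history including age and smoking history will be obtained within 2 weeks of randomization" and "Physical examination including height and weight will be recorded within 2 weeks of surgery". The preoperative list in section 8.0 includes "Risk Factors: smoking, obesity (BMI > 30". None of these places says what the factors are risk factors for, and none mentions drain time.

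**The concern.** The trial is small, the type I error is strict at .01, and two baseline variables labelled as risk factors are on file for every patient at no extra cost. If they predict drain time, a linear model of drain time on treatment, BMI and smoking estimates the same mean difference with a smaller standard error. Leaving them out would then give up precision. A second worry is that, if covariates are not mentioned, someone could choose them after seeing the outcomes. At stake is power for the 4 day difference, and a possible loophole in the primary analysis.

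**Working it through.** **Inputs.** From section 9.0: difference 4 days, N = 90, cutoffs 3.64, .632 and 2.57, power .95. Assumed, because the documents do not say: 1:1 allocation (45 per arm), interim at half the information (supported by 2.57 × √2 = 3.63, close to the printed 3.64), and R², the share of variance explained by the two covariates. The SD is not stated either, so it is solved for.

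**1. Reproduce the plan's design.** Integrating the two-look rule under no difference gives a two-sided type I error of .0100, as stated. Inflation for inevaluable patients: 90 / (1 − .05) = 94.7, rounded up to 95, as stated. Power .95 needs an expected final Z of 4.247. With Z = 4 / (SD × √(2/45)) = 18.97 / SD, the implied SD is 18.97 / 4.247 = 4.47 days. The .95 is matched by construction; the .01 and the 95 are independent checks.

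**2. Effect of adjusting for two covariates.** The variance of the treatment estimate is multiplied by (1 − R²) × 87/85. The factor 87/85 is the price of fitting two extra terms with 90 patients. So

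- adjusted expected Z = 4.247 / √[(1 − R²) × 87/85]
- patient-equivalent = 90 / [(1 − R²) × 87/85]
- break-even: (1 − R²) × 87/85 = 1, so R² = 2/87 = .023

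| Assumed R² | Expected Z | Patient-equivalent | Power | Change (points) | Change, paired simulation |
|---|---|---|---|---|---|
| 0 | 4.198 | 87.9 | .945 | −0.5 | −0.6 |
| .05 | 4.307 | 92.6 | .956 | +0.6 | +0.5 |
| .10 | 4.425 | 97.7 | .966 | +1.6 | +1.7 |
| .20 | 4.693 | 109.9 | .981 | +3.1 | +3.3 |

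In the simulation the break-even R² is about .03. Below it, adjustment loses power.

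**3. Dependence on the SD.** Same formula, with SDs on both sides of the implied value. 3.7 is the treated-arm figure of the phase II breast-cancer trial described in section 2.0; 6 is an assumed value.

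| SD | Unadjusted power | Change at R² = 0 | .05 | .10 | .20 |
|---|---|---|---|---|---|
| 3.7 | .994 | −0.1 | +0.1 | +0.3 | +0.5 |
| 4.47 | .950 | −0.5 | +0.6 | +1.6 | +3.1 |
| 6 | .72 | −1.2 | +1.5 | +4.3 | +10.0 |

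At SD 1.70, another treated-arm figure in section 2.0, power is essentially 1 and the change is zero.

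**4. The 21-day limit.** Section 7.1 removes drains when the output criterion is met "or a maximum of 21 days for axillary node dissection", so drain time is not normal. Simulating whole-day times capped at 21, with a pooled SD of 4.3, gives −0.6, +0.4, +1.3 and +2.8 points at R² of 0, .05, .10 and .20. The picture does not change.

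**5. Type I error.** With the variance estimated from the data and the printed normal cutoffs, simulation gives about .012 for the unadjusted and for the adjusted test. Adjustment neither causes nor cures this small excess.

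**6. Is the choice left open?** No. A two-sample Z contains no covariates, so naming it settles that none enter the primary comparison.

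**The case for a change.** The strongest case for adjusting is an asymmetry. Across the scenarios simulated, the loss if the covariates are useless is 0.6 to 1.4 points, about two patients' worth. The gain grows when the SD is larger than the design implies, and section 9.0 gives no SD. The cited phase II trial reports spreads of 9.6 and 3.7 days, whose root mean square is √[(9.6² + 3.7²)/2] = 7.27. At that SD unadjusted power is about .51, and R² = .10 would add about 4.3 points. The cost is a few sentences.

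The arithmetic stands, but the inference does not follow. First, the gain needs a positive R² above the break-even, and nothing in the documents supports one. The section 8.0 label does not say what the two factors predict; the same section records wound complications, so it may refer to those. Age, surgeon and indication for surgery are also recorded, and the documents give no ground for preferring smoking and BMI to them. Second, where the SD is large, adjustment is not the remedy: at SD 6, R² = .10 moves power from .72 to .76, and at 7.27 from .51 to .55. That would be a problem of sample size and of the unstated SD, which is a separate matter. Third, SDs below 4.47 also appear in section 2.0, and there adjustment does almost nothing. Those are breast-cancer trials and serve as context only, whether the SD quoted is large or small.

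**Conclusion.** The concern does not hold. The unadjusted two-sample Z is valid under randomization, addresses the stated difference in means, and is prespecified for both looks. Replacing it with a model adjusted for BMI and smoking would change power by about −0.5 to +1.6 points for R² between 0 and .10 at the implied SD of 4.47 days, and by almost nothing at smaller SDs. Gains above about 3 points need a larger SD, a larger R², or both, and the documents support neither. A team with its own data showing that these factors predict drain time could reasonably prefer adjustment; a team without such data is right to leave the test as it is. The figures rest on 1:1 allocation, an interim at half the information, two covariate terms and 90 evaluable patients. The conclusion itself rests mainly on the validity of the stated test and on the absence of any documented link between the covariates and drain time.

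### Normal-theory cutoffs on a mean-difference Z with estimated variance give an overall type I error of about .012, not the stated .01 (minor, mostly from the final look)

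*Combined protocol and SAP*

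**What the plan says.** Section 9.0 of the combined protocol and SAP describes the design as follows: "A group-sequential design with up to two tests using O'Brien-Fleming early stopping boundaries for both superiority and futility will be used". The error rates are given as "overall type I error probability .01 and power .95 will be used".

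The test is identified only by the phrase "Based on a two-sample Z-score test statistic". Its boundaries are "the interim test cutoffs will be +/- 3.64 to reject the null hypothesis of no difference and +/- .632 to stop for futility", then "with a final test cutoff of +/- 2.57 to reject the null". The target effect is on the mean: "The goal will be to detect a 4 day drop in mean time-to-drain removal". The evaluable sample size is 90, from 95 accrued.

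Section 9.0 gives no SD, variance estimator, t reference or small-sample adjustment. It does not give the interim timing, and neither it nor Section 5.1 gives the allocation ratio.

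**The concern.** The cutoffs are normal quantiles. They deliver the stated error exactly only if the standard error of the mean difference is known. With no SD in the plan, the standard error has to come from the trial data: about 22 to 23 patients per arm at the interim and 45 per arm at the end. The resulting statistic has heavier tails than the normal, so fixed normal cutoffs are crossed slightly too often when there is no treatment effect.

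At stake is whether the design has the error rate that it states. The plan chose a strict level and cutoffs tuned to it, so the departure is worth correcting even though it is small. The unnamed statistic also matters: two analysts could compute different Z-scores and decide differently near a boundary.

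**Working it through.** **Inputs from Section 9.0.** Cutoffs 3.64 (reject) and .632 (futility) at the interim, 2.57 at the end; overall error .01, two-sided because the cutoffs carry +/-; power .95; 90 evaluable patients; 4 days on the mean. Sections 5.3 and 7.1 limit drain time to 21 days.

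**Assumptions.**
- Allocation 1:1, so 45 per arm.
- Interim at half the information, about 45 patients. The cutoffs suggest this: 3.64 / 2.57 = 1.416, close to sqrt(2) = 1.414, the O'Brien-Fleming ratio for two equally spaced looks.
- The statistic is the difference in means divided by its estimated standard error.

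**Step 1: reproduce the plan's figure.** With known variance, (Z1, Z2) is bivariate normal with correlation sqrt(0.5). The error is

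P(|Z1| > 3.64) + P(.632 < |Z1| < 3.64 and |Z2| > 2.57).

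Numerical integration gives .0100 with binding futility (.0103 non-binding). The first term is .00027. The plan's .01 reproduces, so the boundaries themselves are correctly computed for a true normal Z.

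**Step 2: tail areas at each look with estimated variance.**

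| Look | Cutoff | Normal | t |
|---|---|---|---|
| Interim (43 df) | 3.64 | .00027 | .00073 |
| Final (88 df) | 2.57 | .0102 | .0119 |

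**Step 3: both looks together.** Null trials were simulated with an estimated-variance statistic at 22 or 23 per arm and then 45 per arm (4 to 8 million trials per setting for normal data; 1 to 2 million for the other rows).

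| Outcome and statistic | Overall error, binding futility |
|---|---|
| Normal, mean difference | .0119 to .0120 |
| Normal capped at 21 days, mean difference | .0121 |
| Skewed whole-day times capped at 21 (lognormal, exponential), mean difference | .0123 to .0125 |
| Uncapped skewed (lognormal, exponential), mean difference | .0103 to .0105 |
| Rank-based (Wilcoxon) Z | about .0096 |

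Non-binding futility raises these slightly: .0122 to .0124 for normal data, and about .0107 for the uncapped exponential.

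**Step 4: where the excess arises.** For normal data the total excess is about .0119 - .0100 = .0019. The interim contributes .00073 - .00027 = .00046, and .00046 / .0019 is about one quarter. The remaining three quarters come from the final look.

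**Step 5: unstated inputs.** Interim looks at 18 to 30 per arm give .0117 to .0121, and 1:2 allocation gives .0119. The result does not depend on the two design assumptions.

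**Step 6: t cutoffs.** The nominal two-sided levels are .00027 and .0102. The t quantiles at these levels are 3.97 (43 df) and 2.63 (88 df). Simulation with 3.97 / .632 / 2.63 returns an overall error of .0100.

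**Step 7: power.** Solving the known-variance design for power .95 gives a drift of 4.247, so the implied SD is 4 / (4.247 x sqrt(2/45)) = 4.47 days. At that SD, simulated power falls from about .946 to .948 with the plan's cutoffs to about .940 to .942 with the t cutoffs.

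**The case against.** The best objection is that the premise is inferred. Section 9.0 names no estimator. It also describes the outcome as a time to event and quotes a historical median, so a rank-based or log-rank Z is a possible reading. Under a Wilcoxon Z the excess disappears. A log-rank Z simulated on whole-day times limited at 21 days gave about .011, roughly half the excess. This stands as a limit on the claim, but the mean-based reading is the more natural one because the stated goal is a drop in the mean.

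The second objection is size. The excess is 0.2 percentage points, .012 rounds to the stated .01, and normal boundaries are an ordinary large-sample approximation. A decision would change only for an interim |Z| between 3.64 and 3.97 or a final |Z| between 2.57 and 2.63. This also stands, and it is why the point is minor.

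Third, the degrees of freedom rest on an allocation ratio and an interim time that the plan does not state. That is correct, so they should be taken from the actual numbers at each look.

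A reader might infer something stronger: that the small interim sample breaks the error control, because the chance of a false interim rejection is nearly three times what was intended. The ratio is right (.0007 against .0003), but both probabilities are very small and the interim adds only about .0005. A reader might also infer that the boundaries were miscalculated. They were not; they give .0100 for a normal Z.

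**Conclusion.** The point holds as a minor one. If the statistic is a difference in means with estimated variance, the plan's cutoffs give an overall two-sided type I error of about .012 (.0119 to .0125 for normal data or data capped at 21 days) instead of .01. For uncapped skewed data it is about .0103 to .011. Most of the excess comes from the final look.

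The conclusion assumes 1:1 allocation and a half-information interim, though it changes little when these vary. It depends more on the choice of statistic: it does not apply to a rank-based Z. The documents therefore do not support saying without qualification that the trial's error rate is .012, because the plan leaves the statistic unnamed.

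**What to change.** Add one sentence to Section 9.0 stating that the test statistic is the difference in mean time to drain removal divided by its estimated standard error, and that it is referred to the t distribution at the nominal levels of the present rejection cutoffs, with degrees of freedom from the actual numbers at each look. Under the assumptions above, the cutoffs would be about 3.97 (43 df) at the interim and 2.63 (88 df) at the end. The futility cutoff can stay at .632.

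Either of two alternatives would also do: compare the statistic with its re-randomisation distribution at the same nominal levels, or keep the cutoffs and restate the overall type I error as about .012. If a rank-based or log-rank test was intended, the plan should say so, and the t cutoffs should not be used.

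The t reference needs no extra patients and costs about 0.6 to 0.7 percentage points of power at an SD of 4.47 days. That SD is solved back from the design's own power, so it is not independent evidence of the true variability.

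### Does leaving the time of the single interim test unstated put the planned power at risk?

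*Combined protocol and SAP*

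**What the plan says.** Section 9.0 (Statistical Considerations) is the only place that describes the interim test. It fixes:

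- the number of looks and the boundary type: "A group-sequential design with up to two tests using O'Brien-Fleming early stopping boundaries for both superiority and futility will be used"
- the error rates: "overall type I error probability .01 and power .95 will be used"
- the interim rule: "the interim test cutoffs will be +/- 3.64 to reject the null hypothesis of no difference and +/- .632 to stop for futility"
- the final rule: "with a final test cutoff of +/- 2.57 to reject the null"
- the size: "A maximum of 95 patients will be accrued to obtain a sample size of 90", and the pace: "with an accrual rate of 7 patients per month"

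It gives no patient count, information fraction or date for the interim test. It does not say whether a trigger would count enrolled patients, evaluable patients, or patients whose drain-removal time is known. The last distinction matters a little because, under section 5.3, the drain may stay in "for 2 days or maximum of 21 days has elapsed since surgery".

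**The concern.** Fixed cutoffs do not adapt to the time of the look, as an error-spending function would, so the same futility cutoff of .632 means different things at different times. Under no effect, P(|Z| < .632) = .473, so nearly half of such trials would end at the interim. Under the design effect, a wrong futility stop has probability 0.9% at half information, 3.3% at one third and 6.5% at one quarter. Within the futility zone, the chance that the trial would still have ended in a benefit claim runs from 10% to 50% at half information, but from 45% to 78% at one third. A look that early would give up trials that were still about as likely as not, or better, to succeed. An unwritten time could also be chosen after data have been seen.

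**Working it through.** **Inputs.** From section 9.0: interim cutoffs 3.64 (reject) and .632 (futility), final cutoff 2.57, alpha .01, power .95, 90 evaluable of 95 accrued, 7 patients per month. From section 5.3: drain time of at most 21 days. Assumptions: equal allocation, and a lag from entry to known drain time of 10 to 21 days.

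**Model.** Let t be the information fraction at the interim and θ the expected final Z under the design effect. Z1 has mean θ√t, Z2 has mean θ, both have variance 1, and their correlation is √t. Reject if |Z1| > 3.64, or if .632 ≤ |Z1| ≤ 3.64 and |Z2| > 2.57.

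**1. The plan's own type I error.** At θ = 0 and t = .5:

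- P(|Z1| > 3.64) = 2 × .000136 = .0003
- P(continue, then |Z2| > 2.57) = 2 × .004867 = .0097
- total .0100, the stated .01

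**2. The time implied by the rejection cutoffs.** With O'Brien-Fleming boundaries, interim cutoff = final cutoff / √t.

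| t | 2.57/√t | Plan |
|---|---|---|
| 1/2 | 3.63 | 3.64 |
| 1/3 | 4.45 | 3.64 |
| 1/4 | 5.14 | 3.64 |

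Solving for t gives (2.57/3.64)² = .4985.

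**3. The time implied by the futility cutoff.** Section 9.0 names the same boundary type for futility. I read this as the usual form, in which the distance below the design effect also scales as 1/√t: θ√t − .632 = (θ − 2.57)/√t. Hence θ = (2.57 − .632√t)/(1 − t).

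- t = 1/2: θ = (2.57 − .447)/.5 = 4.246, and power with the stated cutoffs is .950
- t = 1/3: θ = (2.57 − .365)/.667 = 3.31, and power is .73
- t = 1/4: θ = (2.57 − .316)/.75 = 3.01, and power is .60

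Of these three times, only half information brings all three cutoffs together with the stated .95.

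**4. Power if the look moves.** Solving directly for power .95 at t = .5 gives θ = 4.247, in line with step 3. Holding θ, the cutoffs and N fixed:

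| t | Wrong futility stop | Power | Two-sided alpha |
|---|---|---|---|
| 1/4 | 6.5% | .901 | .0087 |
| 1/3 | 3.3% | .930 | .0093 |
| .4 | 2.0% | .942 | .0097 |
| 1/2 | 0.9% | .950 | .0100 |
| 2/3 | 0.2% | .953 | .0102 |

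Without the futility stop, power is .953 at each of these times, so the loss comes from that rule alone.

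**5. Realistic loose readings.** Known drain times = .95 × (enrolled − 7 × lag/30.44).

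- Look at 45 enrolled: .95 × (45 − 2.3) = 40.6 down to .95 × (45 − 4.8) = 38.2. Information .45 to .42, power .947 to .945.
- Look at six months, 6 × 7 = 42 enrolled: .95 × (42 − 2.3) = 37.7 down to .95 × (42 − 4.8) = 35.3. Information .42 to .39, power .944 to .941.

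Type I error is .0096 to .0099 over this range.

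**6. The limit on power.** The plan gives no standard deviation, so N = 90 cannot be shown to deliver θ = 4.247. With 45 per arm and a 4-day difference, that drift needs SD = 4/(4.247 × √(2/45)) = 4.47 days. At t = 1/2, 1/3 and 1/4, an SD of 4 gives power .98, .97 and .95; an SD of 5 gives .88, .86 and .82. The drop between half and one third is about 1 to 3 points in each case.

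**The case for a change.** The strongest opposing case is that a time inferred from a ratio of cutoffs is not a pre-specified trigger. Nothing is written to stop a look when the data seem convenient, and the futility rule will often decide the trial. Even if half information is accepted, the counting unit stays open. Up to 7 × 21/30.44 = 4.8 patients could enter while the last drain time is awaited, and the plan does not say how they are analysed if the trial stops.

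What stands is that the sentence is missing, and that one naming 45 of 90 evaluable patients with known drain time would do no harm. What does not stand is that the time is open. A look at one third with 3.64 would contradict the boundary named in the same section. There is only one interim look, so the rejection cutoff that fixes its time fixes it for the futility rule as well. The counting unit moves power by under 1 percentage point, a look later than half costs no power, and about five late entrants do not affect whether the stated rules are sound.

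**Conclusion.** No change follows. The omission is real, but it is a missing detail and not an error: no stated cutoff, error rate or patient number is wrong, and an analyst applying the named boundaries would look at about half information. There the type I error is .0100. If the stated .95 holds at half information, plausible departures leave power at .941 to .947. The losses to .93 and .90 need a look at one third or one quarter, which the plan's own boundary excludes.

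This rests on equal allocation, on an approximately normal Z statistic, and on taking the stated power as true. The cutoffs are coherent with .95 at half information, but the adequacy of 90 patients cannot be confirmed without a standard deviation. That is a separate matter from the time of the look.
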